4.1 Eligibility criteria for entry into the study

Inclusion criteria:

A patient will be eligible for inclusion in this study if all of the following criteria apply.

1. Men with prostate adenocarcinoma confirmed on prostate biopsy and with sufficient cancer-containing biopsy tissue surplus to diagnostic need to provide ≥ 2 sections for primary endpoint analysis.
2. Scheduled for open or robotic radical prostatectomy
3. Age ≥ 18 years
4. Eastern Cooperative Oncology Group (ECOG) performance status 0 or 1 (Appendix 1)
5. The patient is willing and able to comply with the protocol scheduled follow-up visits and examinations for the duration of the study
6. Participant is willing and able to give informed consent.
7. Participants whose partner is of child bearing potential must be willing to ensure that they or their partner use effective contraception during the trial and for 70 days thereafter.
8. Adequate haematologic, renal and hepatic function, defined as follows:

Laboratory Test	Value required
Haemoglobin (Hb)	≥ 90 g/L

White Blood Count (WBC)	>2.5 x 10 ⁹ /L
Absolute Neutrophil Count (ANC)	≥ 1.5 x10 ⁹ /L
Platelet count	≥ 100 x 10 ⁹ /L
AST, ALT, and alkaline phosphatase	≤ 2.5 x upper limit of normal
eGFR*	≥30ml/min

*eGFR calculated by Cockcroft & Gault formula, see appendix 2

Exclusion criteria:

A patient will not be eligible for the trial if any of the following apply:

1. Treated with systemic corticosteroids, insulin, metformin, other oral hypoglycemic agent, or anti-androgens in the 28 days prior to first dose of study drug
2. Diabetes mellitus
3. Previous prostate radiotherapy
4. Current or previous treatment with xentuzumab or other IGF or GH -modifying therapy
5. Patients who are known to be serologically positive for Hepatitis B, Hepatitis C or HIV
6. Treatment with any other investigational agent, or treatment in another interventional clinical trial within 28 days prior to enrolment
7. Other psychological, social or medical condition, physical examination finding or a laboratory abnormality that the Investigator considers would make the patient a poor trial candidate or could interfere with protocol compliance or the interpretation of trial results.

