13 STATISTICAL CONSIDERATIONS

13.1 Sample size and power

In a preclinical prostate cancer model, xentuzumab suppressed IGF-1R phosphorylation (pIGF-1R) with an effect size of 0.68 (G*Power v3.1). Using Wilcoxon signed rank test, matched pairs, 2-tailed), recruitment of 20 patients (20 matched pre/post-treatment pairs) will be significant with 80% power, alpha = 0.05. Using a one-tailed test based on the hypothesis that xentuzumab will reduce pIGF-1R, we will need 16 patients, 16 matched pairs of tissue. We will recruit 20-30 patients in case some prostate biopsies are inadequate or unsuitable for translational studies.

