**Table 1: Estimand-to-analysis table template**

**Primary Objective:** Assess the amount of IGF pathway inhibition induced by xentuzumab

**Estimand:** The amount of IGF-1 blockade induced by xentuzumab measured through automated immunohistochemistry (IHC) analysis of IGF-1 receptor activation (phospho-IGF-1R) and downstream activation marker phospho-S6.

**Treatment:** Xentuzumab infusion (1000mg), once weekly for a minimum of 4 weeks

Estimand	Analysis
Target population	Analysis set
Men ≥ 18 years old with prostate cancer who are scheduled for radical prostatectomy.	All participants who meet trial eligibility criteria and initiate treatment.
Variable	Outcome measure
H-Score or % of positively stained cells for phospho-IGF-1R and phospho-S6 as measured by IHC.	Statistical significance of the difference between IGF1 axis activity in PRE treatment and POST treatment samples.  All participants who have sufficient material in the diagnostic (PRE-treatment) and in theatre (POST-treatment) biopsy cores for IHC analysis will be included, provided intercurrent events have not affected their ability to meet trial eligibility criteria.
Handling of intercurrent events	Handling of missing data
Intercurrent events which prevent the patient from having in theatre (POST-treatment) biopsy cores available for IHC analysis after at least 4 doses of xentuzumab will preclude the patient from analysis of the primary endpoint. This does not fall under the	Missing data will not be imputed. Patients whose samples are not sufficient to provide a score at baseline and after treatment will be excluded from the primary endpoint analysis. For other endpoints/analyses, Chief Investigator  Sensitivity analysis: NA, data will not be imputed.

typical handling of intercurrent events due to the single arm design of this trial.

Intercurrent events that do not prevent the patient from having in theatre (POST-treatment) biopsy cores available for IHC analysis, and would not affect the patient's trial eligibility, will be assessed by the Chief Investigator.

Population-level summary measure	Analysis approach

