Sample size calculations were repeated in October 2022 based on newly acquired preclinical data quantifying the amount of IGF axis pathway inhibition achieved by xentuzumab. This equates to the WINGMEN trial primary endpoint: the amount of IGF axis pathway inhibition. In a preclinical prostate cancer model, xentuzumab suppressed IGF-1R phosphorylation (pIGF-1R) with an effect size of 0.68 (G\*Power v3.1). Using Wilcoxon signed rank test (matched pairs, 2-tailed), recruitment of 20 patients (20 matched pre/post-treatment pairs) will be significant at the 5% level with 80% power. Using a one-tailed test, based on the hypothesis that xentuzumab will reduce pIGF-1R, we will need 16 patients (16 matched pairs of tissue). Therefore, we aimed to recruit 20-30 patients in case some prostate biopsies are inadequate or unsuitable for translational studies.

	n	Median serum IGF-1 nmol/l		n	Median serum IGF-1 nmol/l	p value
Benign epithelium						
IGF-1R score ≤ 10	77	16.54	IGF-1R score > 10	60	16.68	p=0.871
Malignant epithelium						
IGF-1R score ≤ 14	79	15.58	IGF-1R score > 14	60	17.07	p=0.038

**Table 2. Serum IGF-1 associates with IGF-1R immunoreactive score in malignant prostate epithelium.** Immunoreactive scores (calculated as described in [3] were divided by the median values. IGF-1R scores were generally higher in malignant epithelium, consistent with our earlier report of IGF-1R overexpression in prostate cancer [4], hence cut point of 14 in malignant epithelium vs 10 in benign epithelium. NB Two samples had no benign epithelium in the scored sections ([name], [name], [name], unpublished).

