- RNA will be extracted from unstained FFPE sections of diagnostic biopsy and in-theatre prostate biopsy cores, initially using freshly cut sections of the two first trial patients identified in Section 3.4, for transcriptional profiling. RNA will be stored in a designated -80°C freezer. If RNA yield and quality are sufficient for sequencing, RNA will be extracted from FFPE sections of the remaining cases and stored at -80°C as above. If RNA yield is insufficient, we will re-review each biopsy with [name] to decide whether we can cut additional sections from some/all of the cases. RNA will be sent on dry ice to Azenta for quality control and sequencing as described in WINGMEN\_DataDefinitions&Tables Section 5.2.2. Final analysis will be performed when RNA-seq data have been accrued from all evaluable trial subjects (i.e. those with sufficient tumour in the diagnostic biopsy to allow within patient comparison with RNA extracted from prostate cancer cores post-xentuzumab).
- Mutation panel screening and TPMRSS2-ERG FISH will be performed on sections of radical prostatectomies as single batches after the samples from the last patient have been collected.
- Phospho-proteomic profiling: fresh frozen punch biopsies taken from unfixed prostatectomies are stored in the Oxford Radcliffe Biobank. Given that we have no matched pre-treatment fresh frozen biopsies, we plan to hold analysis of these samples until the other endpoint analyses have been completed. If sufficient funds remain, and if we can access fresh biopsies from Gleason-matched prostatectomies in non-trial patients, we will analyse tumour lysates by Reverse Phase Protein Array (e.g. Institute of Genetics and Cancer in Edinburgh: [www.ed.ac.uk/cancer-centre/facilities/htpu-microarray-services/reverse-phase-protein-arrays](http://www.ed.ac.uk/cancer-centre/facilities/htpu-microarray-services/reverse-phase-protein-arrays)). The analysis will be performed in a single batch after samples from the last patient have been collected.

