#### 4.1.5 RNA-seq

RNA-seq data will be analysed by [name] and [name], [name] lab bioinformaticians. Analyses will use R Statistical Software and the RStudio integrated development environment. A matrix of gene counts containing all samples will be generated by the process(es) described in WINGMEN\_DataDefinitions&Tables Section 5.2.2. Genes with low counts will be filtered using the filterByExpression function in the edgeR R package [8]. Differential expression analysis will be completed using widely used software packages such as DESeq2, edgeR, and limma [9, 8, 10]. All packages correct for the effect of library size. DESeq2 models genes using a negative binomial generalised linear model and tests the null hypothesis that there is no differential expression across the two sample groups using a Wald test. edgeR also tests for differential expression by fitting a negative binomial model and uses the exact test to identify differentially expressed genes. Limma fits a gene-wise linear model and uses moderated t-statistics to perform hypothesis testing. The p-values are corrected for multiple testing using the Benjamini-Hochberg (BH) method to produce an adjusted p-value. Results will be considered significant at adjusted p-value  $\leq 0.05$ , meaning that the proportion of false positives expected amongst the differentially expressed genes is 5%. If the signal from differential expression analysis is not strong, an adjusted p-value  $\leq 0.1$  may be used. An unfiltered list of ranked genes will be used for gene set enrichment analysis (GSEA) to identify pathways that are activated or suppressed by xentuzumab [9]. The primary database that will be used for GSEA is the Gene Ontology (GO) terms for Biological Processes (BP) [10] and the analysis will be run using the clusterProfiler R package with BH multiple test correction. Depending on results of other analyses (e.g. PBMC immunoprofiling), we may manually select relevant pathways (e.g. immune pathways) from Gene Ontology Biological Processes [10], KEGG [11, 12], BioCarta [13], WikiPathways [14], Reactome [15], and Hallmarks MSigDB [16]. Results of GSEA analysis will be considered significant at an adjusted p-value  $\leq 0.05$  or, if the expression signal is low,  $\leq 0.1$ .

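### No tumour-only denominator is stated for the primary IHC score, and no patient or tumour-fraction term for RNA-seq, so a systematic PRE/POST shift in tissue composition would be read as a drug effect

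*SAP*

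**What the plan says.** **What is scored.** The primary variable in SAP Table 1 is "H-Score or % of positively stained cells for phospho-IGF-1R and phospho-S6 as measured by IHC". SAP 4.1.1 describes the H-Score as built from the percentage of tissue at each staining intensity, on a 0-300 scale, with percentage of positive cells as the fallback. No cell compartment is named. Table 1 admits a patient to the primary analysis if there is enough material in both the diagnostic and the in-theatre cores.

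**How tissue is chosen.** Protocol 4 has tumour content of the diagnostic biopsy checked at the MDT meeting before a man is approached. Inclusion criterion 1 (Protocol 4.1) requires "sufficient cancer-containing biopsy tissue surplus to diagnostic need" to give at least two sections. POST tissue is two or three cores taken in theatre (Protocol 4.8), with no tumour targeting stated. Protocol 6.1 then has a pathologist select blocks from diagnostic biopsies, in-theatre cores and prostatectomies for tumour content, so that biopsy tumour is compared with the index tumour.

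**RNA-seq.** SAP 3.4.3 extracts RNA from unstained FFPE sections, with no dissection step stated, and defines evaluable subjects as "those with sufficient tumour in the diagnostic biopsy to allow within patient comparison". SAP 4.1.5 states: "Differential expression analysis will be completed using widely used software packages such as DESeq2, edgeR, and limma". It describes tests between two sample groups, including the edgeR exact test, and correction for library size.

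**The concern.** A diagnostic biopsy and a core taken from the surgical specimen are different samples of the gland and need not hold the same mix of tumour, benign gland and stroma. If the score is taken over all cells in the section, it depends on that mix as well as on signalling inside tumour cells. The same is true, gene by gene, of RNA from whole sections.

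In a randomised trial a control arm would show the same shift, and it would cancel. SAP 2 and 3.1 make clear that here each patient is his own control, so nothing in the design separates a change in composition from a change due to xentuzumab. The primary conclusion is at stake, in either direction: a lower tumour fraction at POST could mimic pathway inhibition, and a higher one could hide it. The investigators' own earlier data treat compartment as relevant. SAP Table 2 scores malignant and benign epithelium separately, and its legend reports that "IGF-1R scores were generally higher in malignant epithelium".

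**Working it through.** **1. The plan's own figure.** Inputs (Protocol 13.1): standardised paired effect 0.68, Wilcoxon signed rank test, alpha 0.05. With the usual efficiency factor, n′ = n × 3/π, and power comes from the noncentral t with noncentrality 0.68√n′.
- Two-tailed, n = 20: n′ = 19.10, noncentrality 2.97, power 80.3%. This reproduces "recruitment of 20 patients (20 matched pre/post-treatment pairs) will be significant with 80% power, alpha = 0.05".
- One-tailed, n = 16: n′ = 15.28, noncentrality 2.66, power 81.2%. This reproduces "we will need 16 patients, 16 matched pairs of tissue".

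The sample size is sound on its inputs and is not affected by this point.

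**2. Rules on tumour content, side by side.**

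| Step | PRE | POST |
|---|---|---|
| Entry criterion | Yes (Protocol 4, 4.1) | None |
| Targeting when sampled for the trial | Not applicable (diagnostic tissue) | None stated (Protocol 4.8) |
| Block selected for tumour by pathologist | Yes (Protocol 6.1) | Yes (Protocol 6.1) |
| Minimum tumour fraction or tumour-cell count | None stated | None stated |
| Score limited to malignant epithelium | Not stated | Not stated |
| RNA evaluability by tumour sufficiency | Yes (SAP 3.4.3) | Not stated, though the cores are described as cancer |

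**3. Composition artefact with no drug effect.** Let f be the tumour share of scored cells, T the score in tumour cells and B the score in the rest. The section score is S = fT + (1 − f)B, so the spurious change is (f_post − f_pre)(T − B). The documents give none of f, T or B for the phospho-markers. Assume f_pre = 0.60:

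| B/T | f_post 0.50 | 0.40 | 0.30 |
|---|---|---|---|
| 0 | −17% | −33% | −50% |
| 0.25 | −11% | −21% | −32% |
| 0.5 | −6% | −13% | −19% |
| 1 | 0 | 0 | 0 |

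Example, B/T = 0.5: S falls from 0.60 + 0.40 × 0.5 = 0.80 to 0.50 + 0.50 × 0.5 = 0.75, which is −6%. If f rises, or if B exceeds T, the sign reverses.

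**4. What this could do to the test.** Assume T = 150, SD of the change in f 0.20, other paired SD 30 and n = 20. For B = 50 and a mean fall of 0.10, the shift is −10 points, the SD is √((0.20 × 100)² + 30²) = 36.1, and the standardised shift is 0.28. Simulated chance of a significant reduction on a paired t-test, with no drug effect:

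| Mean fall in f | B = 20 | B = 50 | B = 100 |
|---|---|---|---|
| 0 | 3% | 3% | 3% |
| 0.10 | 29% | 22% | 10% |
| 0.20 | 79% | 64% | 26% |

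With no mean change in f the two-sided test keeps its 5% level, so random variation in composition adds noise but no bias. In the other direction, a mean rise of 0.10 at B = 50 would cut a true standardised effect of 0.68 to 0.68 − 0.28 = 0.40 if the SD is unchanged. Power at 20 pairs then drops from 80% to 38%.

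**5. RNA-seq.** The same algebra applies to each gene. A fall in tumour fraction lowers genes expressed mainly in tumour and raises those expressed mainly in stroma or immune cells. Separately, treating pairs as two groups uses variance 2σ²/n for the mean difference in place of 2σ²(1 − ρ)/n. With positive within-patient correlation ρ, this wastes the pairing that SAP 3.4.3 intends. The exact test takes no covariates, so it can hold neither term. No size is given here, because the documents contain no gene-level contrast by compartment.

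**The case against.** The strongest reply has four parts.

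- **POST tissue is selected too.** A reader might infer from the entry criterion that PRE tissue is tumour-rich and POST tissue is unselected. Protocol 6.1 contradicts that, because in-theatre cores are among the blocks selected for tumour content. Surgical specimens of insufficient quantity or quality also make a patient non-evaluable (Protocol 5.1, SAP 6.2). This stands. What remains is that selecting a block neither restores tumour that the cores missed nor says which cells in the block are scored.
- **The direction is not shown.** It is tempting to argue that selecting on PRE makes POST fractions lower and so favours a positive result. Criterion 1 sets an amount of tissue and not a fraction, POST blocks are also chosen for tumour, and no fraction is given at either time. This stands in full.
- **The only compartment figures concern another marker.** The 14 versus 10 cut points and the SD of 3.5 in SAP 3.2 belong to total IGF-1R. The cut points compare malignant with benign epithelium, not with stroma. They cannot size an artefact in phospho-IGF-1R or phospho-S6, and are not used for that here.
- **The detail may be elsewhere.** SAP 1 makes the Data Definitions and Tables document integral to the SAP, and Protocol 6.1 refers tissue analysis to the sample handling manual. Neither was available. Either could define HALO tumour segmentation or RNA dissection, so the finding is limited to what the protocol and SAP state.

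There are also partial safeguards. HALO output is reviewed with the pathologist (SAP 5.6.3.1, 6), who also scores phospho-IGF-1R by subcellular site (SAP 4.1.1), and one untreated PRE/POST pair was compared (SAP 3.4.1). The reviews are not stated to define a tumour-only denominator. The single pair addressed epitope stability and cannot estimate a systematic difference in composition.

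**Conclusion.** The point holds as a gap in specification, not as a demonstrated bias. The protocol and SAP do not state that the primary score is confined to malignant epithelium, set no minimum or matched tumour content for the POST cores, and name neither a patient nor a tumour-fraction term for RNA-seq. In a single-arm PRE/POST design, a systematic difference in tumour fraction would therefore be attributed to the drug.

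Direction and size are unknown. The artefact is zero if mean fractions match or if tumour and non-tumour cells carry equal signal, and it reverses if POST fractions are higher. The figures above rest wholly on assumed fractions, signals and SDs. They show only that a shift of 0.10 to 0.20 could matter at 20 pairs. The documents do not support concluding that the primary endpoint is biased toward success, or that the RNA-seq results are contaminated. The RNA-seq part concerns an exploratory endpoint and carries less weight.

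**What to change.** **SAP Table 1 and 4.1.1.** Compute the H-Score, or percentage positive, only within malignant epithelium annotated by the pathologist. Set the same minimum tumour-cell count for PRE and POST, and report tumour fraction by time point. If the Data Definitions document already specifies this, a cross-reference is enough.

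**SAP 4.1.5.** Replace the two-group test with a paired model (patient + time). Record tumour fraction for each extracted section, from an adjacent H&E section or HALO, and report a sensitivity model that adds it.

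**Cost.** SAP wording, plus a small annotation step on slides the pathologist already reviews; it should be settled before the scores are analysed. A minimum tumour-cell count may lose some pairs. Tumour fraction at POST is measured after treatment, so adjusting for it could mask a drug effect that acts through loss of tumour cells. For that reason the adjusted model is shown beside the unadjusted one and does not replace it.

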7.6 Dose modification

All doses of xentuzumab will be 1000mg with no dose reduction. In the event that a patient experiences unacceptable toxicity at this dose, the patient should be withdrawn from further treatment.

Infusion reactions

In the event of mild to moderate infusion reaction a slower infusion rate may be used, the infusion duration doubled from 1 to 2 hours. Treatment with an antihistamine/corticosteroid may also be given, per standard local policy. Severe infusion reactions require immediate and permanent discontinuation of infusion.

Management of other toxicities

Patients with advanced cancer treated with xentuzumab in previous trials have experienced drug-related adverse events including decreased appetite, nausea, diarrhoea, constipation, fatigue, reduced weight, infusion-related reaction, reduced WBC and hyperglycaemia. The majority of drug-related AEs have been of grade 1-2 (Xentuzumab Investigator Brochure). Refer to the current xentuzumab IB for guidance on management and give symptomatic treatment as appropriate. In the event of unacceptable toxicity, the patient should be withdrawn from further treatment.

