8.3 Prohibited therapies

Patients should not be prescribed any other anti-cancer or investigational therapies while participating in this study. In addition, the following are prohibited:

- Systemic corticosteroids (unless required for treatment of an infusion reaction)
- Insulin, metformin or other oral hypoglycemic agents (unless indicated to manage an adverse reaction of altered glucose metabolism)
- Anti-androgens

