14.1 Inclusion in analysis

Patients with both pre- and post-treatment data will be included in the analysis, regardless of whether or not they completed xentuzumab treatment. All patients will be included in the safety analysis.

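### SAP Table 1 makes inclusion of a complete PRE/POST pair depend on entry criteria still being met after dosing, an exclusion found nowhere else in the plan

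*SAP*

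**What the plan says.** SAP Table 1 defines the analysis set as participants who meet the eligibility criteria and start treatment. Its outcome-measure cell then includes men with enough tissue at both time points, but only "provided intercurrent events have not affected their ability to meet trial eligibility criteria". The cell on intercurrent events repeats the condition. Events that leave POST cores available and "would not affect the patient's trial eligibility, will be assessed by the Chief Investigator". No criterion, timing or consequence of that assessment is given. The same cell bars from the primary analysis men whose events prevent POST cores being available after at least 4 doses.

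The rest of the plan reads differently:

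- **Protocol 4.4 and 4.7:** eligibility is checked in the 7 days before dose 1 and confirmed at registration, before treatment.
- **Protocol 14.1:** "Patients with both pre- and post-treatment data will be included in the analysis, regardless of whether or not they completed xentuzumab treatment".
- **Protocol 5.1 and SAP 6.2:** both list the men who are not evaluable for the primary endpoint. The grounds are fewer than 3 doses, no prostatectomy, predominantly neuroendocrine or small cell cancer, inadequate specimens, and surgery more than 6 days after the last dose. Loss of eligibility during treatment is not among them.
- **Protocol 5.1 and 7.4:** men who miss doses for unavoidable reasons may stay on trial if weekly dosing resumes and the last dose falls within 6 days of surgery.

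**The concern.** Eligibility describes a man at entry. An intercurrent event happens after treatment starts. The analysis set already requires eligibility, so the proviso adds something only if entry criteria are tested again after dosing.

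Several criteria in Protocol 4.1 carry no date and can then fail: the white cell, neutrophil and AST/ALT limits, ECOG 0 or 1, and ability to comply with visits for the whole study. Protocol 7.6 names fatigue among the drug-related events, together with "infusion-related reaction, reduced WBC and hyperglycaemia". Missed doses bear on the compliance criterion although the protocol tolerates them.

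The trial has no control arm, and the PRE/POST difference is its only contrast. Removing complete pairs because of something the drug did leaves a set selected by treatment, and the direction of any bias is unknown. Safeguards against choosing with knowledge of results are thin. The trial is open label, some laboratory members know which samples are PRE and POST (SAP 3.5), and the SAP is dated June 2024, after recruitment ended by Q1 2023 (SAP 1.2 and 3.4.4). SAP 6.3 offers no analysis that would put removed pairs back.

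**Working it through.** **Step 1: can the proviso act at all?** Each rule against the time it refers to:

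| Place | Rule | Refers to |
|---|---|---|
| Protocol 4.4, 4.7 | eligibility confirmed | before dose 1 |
| Protocol 14.1 | pre and post data suffice | whole study |
| Protocol 5.1, SAP 6.2 | listed non-evaluable grounds | whole study; none is lost eligibility |
| SAP Table 1 | pair kept only if events left eligibility unaffected | after dose 1 |

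Table 1 alone ties inclusion to eligibility after dosing.

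**Step 2: reproduce the planned size.** Inputs from Protocol 13.1: "xentuzumab suppressed IGF-1R phosphorylation (pIGF-1R) with an effect size of 0.68"; "Using Wilcoxon signed rank test, matched pairs, 2-tailed"; "recruitment of 20 patients (20 matched pre/post-treatment pairs) will be significant with 80% power, alpha = 0.05". The normal-parent efficiency 3/π for the Wilcoxon test is my assumption.

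- Effective n: m = n × 3/π. Degrees of freedom: m − 1. Noncentrality: 0.68 × √m.
- Power = P(|T| > t₀.₉₇₅), with T noncentral t.
- n = 20: m = 19.10, df = 18.10, noncentrality = 0.68 × 4.370 = 2.972, critical value 2.100, power 0.803.
- One-tailed with n = 16: power 0.812.

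Both stated sizes (20 and 16) reproduce. Simulating the Wilcoxon test at n = 20 also gives 0.803.

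**Step 3: power if pairs are removed.** The documents give no exclusion rate, so 1 to 3 of 20 is an assumed range.

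| Pairs left | Noncentrality | Power (Wilcoxon) | Power (paired t) |
|---|---|---|---|
| 20 | 2.972 | 0.803 | 0.822 |
| 19 | 2.896 | 0.780 | 0.800 |
| 18 | 2.819 | 0.755 | 0.776 |
| 17 | 2.740 | 0.727 | 0.749 |

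The paired-t column uses m = n; the noncentralities shown are for the Wilcoxon column.

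**Step 4: selection, as a bound.** Simulate 20 standard normal differences with no true effect, drop the k least-inhibited men, and apply a two-sided paired t-test at 0.05.

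| Dropped | Type I error, worst case | Type I error, removal unrelated to outcome |
|---|---|---|
| 0 | 0.05 | 0.05 |
| 1 | 0.09 | 0.05 |
| 2 | 0.16 | 0.05 |
| 3 | 0.26 | 0.05 |

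The worst case assumes that removal picks out exactly the least-inhibited men. It is a limit, not a forecast.

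**The case against.** **The SAP may mean something narrower.** Eligibility may be a slip for evaluability. Adenocarcinoma is an entry criterion, so the proviso might be meant for men whose prostatectomy shows neuroendocrine or small cell cancer. SAP 4.2 sends population definitions to Section 3 of a Data Definitions document that was not supplied. SAP 5.2 is inclusive, since samples from early withdrawers are still used with consent. The missing document is a real limit on certainty. The neuroendocrine reading does not rescue the wording: that case is already listed, and a histological finding at surgery is not an intercurrent event.

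**The practical effect may be small.** Protocol 7.6 says most drug-related events were grade 1–2, and no link between such events and tumour phospho-signal is shown. Recruitment of 20–30 leaves a margin, though its stated purpose is inadequate biopsies. By paired t, 19 pairs still give 0.80. With 25 pairs, losing three leaves 22 and a power of 0.86 (paired t) or 0.84 (Wilcoxon). All of this stands, and power is the lesser issue.

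**Two stronger readings are tempting and unsupported.** A reader might infer that steroids for an infusion reaction, or glucose-lowering drugs for an adverse reaction, both allowed by Protocol 8.3, would cost a man his place through exclusion criterion 1. That criterion covers only the 28 days before the first dose, so on-study use does not breach it. The infusion-reaction counts in Protocol 10.4 therefore measure no exclusion rate. A reader might also infer that the Chief Investigator may remove pairs at will. The clause says that events are assessed; it does not say that pairs are removed.

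**Conclusion.** The point holds as a defect of wording that should be corrected. Followed literally, SAP Table 1 can take complete PRE/POST pairs out of the primary analysis because of drug-related changes in undated entry criteria or tolerated missed doses. That contradicts Protocol 14.1 and adds a ground missing from Protocol 5.1 and SAP 6.2.

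Its size cannot be estimated. One pair lost from 20 costs about 2 points of Wilcoxon power, and three cost about 8. The inflation of type I error depends wholly on how removal relates to outcome, from none to the worst-case figures above. These figures rest on 20 available pairs, normally distributed differences and, for power, the planned effect size of 0.68. Nothing shows that any man was excluded, and the Data Definitions document may define the population differently.

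**What to change.** 1. In SAP Table 1, delete the proviso from the outcome-measure cell and the matching eligibility wording from the intercurrent-event cell.
2. State that eligibility is judged once, on data up to registration. Every evaluable PRE/POST pair then stays in the primary analysis, whatever happens on treatment, unless the man is on the non-evaluable list of Protocol 5.1 and SAP 6.2.
3. State that the Chief Investigator's assessment of other events is descriptive and removes no pairs, or that it is made before PRE/POST scores are seen.
4. Reconcile the dose minimum: Table 1 refers to at least 4 doses, while Protocol 5.1 and SAP 6.2 treat fewer than 3 as non-evaluable. Reconcile Protocol 14.1, which includes men whether or not they completed treatment, with that list. The sponsor must settle which rule governs.
5. Check that Section 3 of the Data Definitions document agrees.

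A sensitivity analysis omitting men given systemic corticosteroids or glucose-lowering drugs between dose 1 and surgery is optional. The cost is SAP wording and at most one extra run, with no new data. The planned 20 pairs are unchanged. A small downside is that a few retained POST samples may carry the effect of a concomitant event.
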